## **Abbreviations and Definitions**

AE	Adverse event
ANCOVA	Analysis of covariance
CCC	Clinical Coordinating Center
CI	Confidence interval
COVID-19	Coronavirus Disease 19
CRF	Case report form
CRP	C-reactive protein
DAS	Disease activity score

DCC	Data Coordinating Center
DLCO	Diffusing capacity of lung for carbon monoxide
% DLCO	Percent predicted diffusing capacity of lung for carbon monoxide
DSMB	Data Safety Monitoring Board
eCRF	Electronic case report form
ESR	Erythrocyte sedimentation rate
FEV1	Forced expiratory volume in one second
FVC	Forced vital capacity
%FVC	Percent predicted forced vital capacity
HRCT	High resolution computed tomography
HRQOL	Health Related Quality of Life
ILD	Interstitial Lung Disease
IMP	Investigational Medicinal Product
IPF	Idiopathic pulmonary fibrosis
ITT	Intention to treat
LCQ	Leicester Cough Questionnaire
ln	Natural logarithm
MedDRA	Medical Dictionary for Regulatory Activities
mg	Milligram
mg/d	Milligrams per day
mL	Milliliter
mm Hg	Millimeters of mercury
msec	Millisecond
OMERACT	Outcome Measures in Rheumatology
PF	Pulmonary fibrosis
PFS	Progression-free survival
PRO	Patient reported outcomes
RA	Rheumatoid arthritis

RA-ILD	Rheumatoid arthritis-associated interstitial lung disease
RAPID3	Routine Assessment of Patient Index Data 3
SAE	Serious adverse event (AE)
SAS	Statistical Analysis Software
SGRQ	St. George's Respiratory Questionnaire
SpO2	Peripheral capillary oxygen saturation
TLCO	Transfer capacity of lung for carbon monoxide
ULN	Upper limit of normal
wk	Week

## **Introduction**

### **Preface**

Rheumatoid arthritis-associated interstitial lung disease (RA-ILD) is a life-threatening and severely debilitating disease characterized by poor survival and a lack of efficacious therapeutic options. Results from previous controlled trials suggest that pirfenidone treatment is safe and well tolerated in idiopathic pulmonary fibrosis (IPF) with efficacy in a variety of domains that include fibrosing ILD. Pirfenidone may be of benefit in RA-ILD, which shares many histopathological and clinic-epidemiological features with IPF. Given the loss of pulmonary function over time in patients with RA-ILD, this protocol is designed to evaluate whether pirfenidone 2403 mg/d reduces decline in forced vital capacity (FVC) or mortality over 52 weeks, compared with placebo, in patients with RA-ILD.

TRAIL1 is a Phase 2, randomized, double blind, placebo controlled clinical trial designed to evaluate the efficacy and safety of administering pirfenidone or placebo for 52 weeks to patients with RA-ILD. Patients meeting the eligibility criteria for the study have been randomized to receive either pirfenidone 2403 mg/d or placebo. Efficacy will be evaluated through pulmonary function tests, patient reported outcomes (PROs), adverse events and survival. Safety will be assessed by

determining differences between the treatment arms for the rate of adverse events, serious adverse events, rates of acute exacerbation, hospitalization and all- cause mortality.

## **Scope of the Statistical Analysis Plan (SAP)**

These analyses will assess the efficacy and safety of pirfenidone 2403 mg/day as compared with placebo in patients with RA-ILD. This SAP assumes familiarity with the TRAIL1 Clinical Trial Protocol, including amendments. In particular, the SAP is based on the planned analysis specification as written in the protocol Section 10 “Statistical Considerations.” Readers may consult the protocol for more background information on the design and conduct of the trial, and planned analyses.

## **Study Objectives and Endpoints**

### **Study Objectives**

To assess the efficacy and safety of pirfenidone 2403 mg/day as compared to placebo in patients with RA-ILD.

To explore the role of peripheral blood biomarkers in predicting disease progression and survival in patients with RA-ILD.

To explore a spectrum of validated questionnaires to assess disease specific PROs including overall health, and perspectives on symptoms, performance and quality of life.

### **Endpoints**

#### **Primary Endpoint**

The primary outcome variable of this study is the incidence of the composite endpoint of decline from baseline in percent predicted FVC of 10% or greater or death during the study period. The primary endpoint will be analyzed using the ITT population

#### **Secondary Endpoints**

Secondary outcome for this study will be assessed from baseline to the end of study for each patient. The following secondary outcomes will be analyzed using the ITT population:

1. Incidence of a decline from baseline in percent predicted FVC of 10% or greater during the study period.
2. Frequency of progressive disease as defined by Outcome Measures in Rheumatology (OMERACT): Relative decline from baseline in percent predicted FVC of  $\geq 10\%$ , or relative change from baseline in percent predicted FVC  $\geq 5\%$  and  $< 10\%$ , and  $\geq 15\%$  relative decline in diffusing capacity of lung for carbon monoxide (DLCO) (Khanna, Mittoo et al. 2015)
3. Change from baseline to end of study in absolute value of FVC
4. Change from baseline to end of study of percent predicted FVC
5. Slope of percent predicted FVC over 52-week treatment period
6. Slope of absolute value of FVC over study period
7. Time to decline of 10% or greater in percent predicted FVC or death while on study
8. Change from Baseline to end of study in dyspnea, as measured by the Dyspnea 12 questionnaire

The following secondary outcomes will be analyzed using the as-treated population:

9. Proportion of participants with all-cause mortality
10. Proportion of participants with all-cause hospitalization
11. Proportion of participants with hospitalization for respiratory cause
12. Number of acute exacerbations requiring hospitalizations
13. Proportion of participants with and number of treatment-emergent adverse events (AEs)
14. Proportion of participants with and number of treatment-emergent serious adverse events (SAEs)
15. Proportion of participants with and number of treatment-emergent/treatment-related AEs
16. Proportion of participants with and number of treatment-emergent/treatment-related SAEs
17. Proportion of participants with and number of AEs leading to early discontinuation of

study treatment

18. Proportion of participants with and number of treatment-emergent death or transplant

19. Proportion of participants with and number of treatment-emergent RA-ILD-related mortality

## **Exploratory Endpoints**

The following exploratory outcomes will be analyzed using the ITT population:

1. Change from Baseline to end of study in Disease Activity Score (DAS)
2. Change from baseline to end of study in Routine Assessment of Patient Index Data 3 (RAPID3) score
3. Change from Baseline to end of study in Erythrocyte Sedimentation Rate (ESR)
4. Change from Baseline to end of study in C-Reactive Protein (CRP)
5. Candidate biomarker expression in the peripheral blood of patients with RA-ILD over the 52 weeks of treatment.
6. Changes from Baseline to end of study in high resolution computed tomography (HRCT) parameters evaluated by quantitative functional imaging
7. Changes from Baseline to Week 13, 26, 39 and final visit in the St. George's Respiratory Questionnaire (SGRQ)
8. Changes from Baseline to Week 13, 26, 39 and final visit in Dyspnea 12 questionnaire
9. Changes from Baseline to Week 13, 26, 39 and final visit in Leicester Cough Questionnaire (LCQ)
10. Changes from Baseline to Week 13, 26, 39 and final visit in the Patient global assessment
11. Changes from Baseline to Week 13, 26, 39 and final visit in the Health assessment questionnaire

## **Study Methods**

### **General Study Design and Plan**

This parallel-group double-blind randomized longitudinal study was designed to assess the superiority of Pirfenidone versus placebo, over a 52-week follow-up period. Patients are randomized with equal probability to receive Pirfenidone or placebo. After the screening visit, randomization occurs at visit 2. The week 52 visit is visit 11. Adverse events are additionally queried by phone 28 days after visit 11.

## **Inclusion-Exclusion Criteria and General Study Population**

Eligible participants include patients age 18 through 85 years, with RA and ILD, without evidence or suspicion of an alternative diagnosis that may contribute to their ILD. Additional details to be found in the protocol.

## **Randomization and Blinding**

After consent was obtained, participants were screened to determine eligibility. After participants were determined to be eligible, they were randomized with equal probability to receive either Pirfenidone or placebo in a double-blinded fashion. Treatment assignment slots were not re-used; each consecutive randomized participant received the next consecutive unused treatment assignment slot. Randomization was stratified by center with random block sizes. The password protected computer text file that contained the translation of treatment labels A and B to either Pirfenidone or placebo was maintained by the unblinded DCC statistician. Details will be provided in the final study report.

## **Study Assessments**

The schedule of all study assessments is in **Appendix A** of the protocol. Eligibility and randomization take place at Visit 2. Time windows for visits are below. There is an additional phone visit that occurs 28 days after the last study drug dose to assess vital status and adverse events.

Visit Number	Visit Week	Target Day of Visit	Visit Window
1	-8 to 0	-56 to 0	-56 to 0 days
2	0	1	0
3	1	7	± 2 days
4	2	14	± 2 days
5	4	28	± 1 week
6	8	56	± 1 week
7	13	91	± 2 weeks
8	19	133	± 1 week
9	26	182	± 2 weeks
10	39	273	± 2 weeks
11*	52	364	± 1 week

\* Visit 11 marks the end of the follow-up period. Protocol amendment V8 (US/CAN/AUS) /V10 (UK) extends the visit 11 window to ± 4 weeks due to COVID-19 laboratory closures.

## Definition of Baseline

Baseline values for spirometry are defined as the screening values. Spirometry is repeated at randomization to ensure stability of values, as defined in the study protocol, prior to randomization. Baseline is defined as screening because the screening spirometry must meet established criteria for quality and is done before and after bronchodilator administration. The underlying true spirometry values are assumed to be the same at randomization. The absolute differences between the measured screening and randomization spirometry values will be summarized descriptively.

Baseline values for patient reported outcomes are defined as the randomization visit values, and when unavailable, the screening or rescreening values will be used. Baseline for other variables is defined as the randomization values for variables collected at randomization, otherwise it is defined as the screening values.

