## **5 STUDY ENROLLMENT AND WITHDRAWAL**

### **5.1 PARTICIPANT INCLUSION CRITERIA**

Subjects must meet all of the inclusion criteria and none of the exclusion criteria to be eligible for this study.

Patients must fulfill all of the following criteria to be eligible for enrollment in the study:

1. Age 18 through 85 years, inclusive, at Screening

2. Probable or definite diagnosis of RA according to revised 2010 ACR/EULAR criteria, without evidence or suspicion of an alternative diagnosis that may contribute to their interstitial lung disease.
3. Diagnosis of ILD
  - a. supported by clinically indicated HRCT, and when available, surgical lung biopsy (SLB), prior to Screening, and
  - b. presence of fibrotic abnormality affecting more than 10% of the lung parenchyma, with or without traction bronchiectasis or honeycombing, on Screening and confirmed by adjudicated HRCT prior to Baseline
4. No features supporting an alternative diagnosis on transbronchial biopsy, or SLB, if performed prior to Screening
5. Attainment of the following centralized spirometry criteria (based on local spirometry on standardized equipment and centralized quality controlled):
  - a. percent predicted FVC  $\geq$  40% at Screening
  - b. change in pre-bronchodilator FVC (measured in liters) between Visit 1 (Screening) and Visit 2 (Randomization) must be a  $<10\%$  relative difference, calculated as:  
 $100\% * [\text{absolute value (Visit 1 FVC} - \text{Visit 2 FVC)} / \text{Visit 1 FVC}]$
  - c. percent predicted DLCO or TLCO  $\geq 25\%$  at Screening
  - d. Screening (Visit 1) pre-bronchodilator(BD) and Post-BD spirometry meets ATS quality criteria as determined by a central reviewer
  - e. Baseline (Visit 2) Pre-BD spirometry meets ATS quality criteria as determined by the site Investigator or the central reviewer
6. Able to understand and sign a written informed consent form.
7. For women of childbearing potential: agreement to remain abstinent (refrain from heterosexual intercourse) or use two adequate methods of contraception, including at least one method with a failure rate of  $<1\%$  per year, during the 52 week treatment period and for at least 118 days after the last dose of study drug.

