### Spirometry and DLCO/TLCO Measurements

All equipment, procedures, and personnel qualifications for the assessment of lung function are based on the recommendations of the American Thoracic Society (ATS 2005) and will be performed and interpreted in accordance with published guidelines (Crapo 1994):

Spirometry measurements will include FVC and FEV1 before and 10-15 minutes after administration of a bronchodilator [albuterol (or salbutamol) from a metered dose inhaler] at screening. The remainder of the spirometric studies will be performed without bronchodilator administration.

Lung volume measurements will be performed by body plethysmography and should be performed before or at least 30 min after the last bronchodilator puff.

DLCO/TLCO will be measured by determining the diffusing capacity of the lung for carbon monoxide.

DLCO/TLCO measurement should be performed before or at least 30 min after the last bronchodilator puff.

All FVC data collected throughout the study will be evaluated by a central reader blinded to treatment assignment. Data for FVC and FEV1, will be entered electronically into the vendor's database and incorporated into the clinical database. DLCO/TLCO will be entered into the clinical database by the site.

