#### *Screening (Visit 1)*

The Screening period (Visit 1) is defined as the time between the date of the first Screening procedure and Eligibility/Randomization (Visit 2) and may last up to 56 days. Screening procedures may be conducted on different days within the Screening period if convenient.

The following procedures will be performed during Screening:

1. Written informed consent
2. Directed medical history/review of systems, review of AEs/SAEs, concomitant medications, oxygen use

3. Physical examination, vital signs, resting oxygen saturation, weight, and height
4. Clinical laboratory assessments, including hematology, serum chemistries, serologic tests, and blood pregnancy test for women of childbearing capacity
5. ECG (obtained before bronchodilator administration or on a separate day)
6. Measurement of Oxygen Saturation at Rest
7. Review of transbronchial biopsy or SLB, if available, to assess eligibility
8. HRCT scan to assess eligibility
9. Spirometry (FVC, FEV1) before and 10-15 minutes after bronchodilator administration
10. Lung volumes, DLCO or TLCO obtained before or 30 minutes after bronchodilator administration
11. Biomarkers (See Appendix A)

*Eligibility and Randomization (Visit 2)*

All Visit 2 procedures must be performed before randomization and before administration of study treatment. Randomization (Visit 2) will occur no more than 56 days after the start of the Screening period, and study treatment should begin on the day of randomization. All results of the screening assessments and eligibility documentation will be submitted to study investigators or designee for approval *at least 2 working days* before the targeted randomization day. Once a participant's documentation is received and the participant is confirmed to be eligible for randomization, the site will be instructed to randomize the participant at the end of Visit 2.

The following procedures will be performed at Visit 2:

*Before Randomization:*

1. Directed medical history/review of systems, review of AEs/SAEs, concomitant medications, oxygen use
2. Physical examination, resting oxygen saturation, vital signs, and weight
3. Pregnancy test for women of childbearing capacity
4. Biomarkers (See Appendix A)
5. Blood samples for genetic research (DNA PAXgene samples) - Optional
6. Spirometry (FVC, FEV1) without bronchodilator administration
7. Patient Reported Outcome Questionnaires (See Appendix A)

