### 10.4.2 Efficacy Analyses

Demographic data and baseline characteristics will be summarized by treatment arm. The primary analysis population will be the ITT population. The main analysis framework will be logistic regression to assess treatment differences in the primary outcome, defined as either death or a decline from baseline of  $\geq 10$  percentage points in percent predicted FVC, reached by week 52. Baseline for spirometry is defined as the screening visit with the assumption that values are the same at randomization. Baseline for other variables is defined as the randomization visit for variables collected at randomization, otherwise as the screening visit. The main predictor will be treatment arm, and covariates known to be related to the outcome and specified a priori (i.e., prior to database lock and unblinding), will be considered for inclusion. The stratification factor will be the site. Unadjusted and adjusted odds ratios, 95% confidence intervals and Wald test p-values will be reported. Similar analyses will be conducted with the listed secondary binary outcomes in Section 4.2.2. An additional secondary analysis of the primary endpoint will use the Per Protocol population.

Statistical analyses of the secondary outcomes that describe time-to-event will use Cox proportional hazards regressions using a similar approach as described above, reporting adjusted hazard ratios, 95% confidence intervals and p-values. Time will be measured from randomization until the event or until censoring. Kaplan-Meier plots will be generated, and proportionality of hazards will be assessed.

There are a number of secondary and exploratory outcome variables that are continuous, that will be calculated for each subject as follows: Each change from baseline to week 52 outcome will be calculated as the last value minus the baseline value. Each slope outcome will be derived from a linear regression of the values over the treatment period. The molecular expression outcomes will involve several genomic approaches to measure gene expression and protein levels with the purpose of identifying candidate biomarkers that differ according to treatment group.

All continuous secondary and exploratory outcomes will be summarized and inspected for unusual outliers and distributional characteristics, and the treatment arms will be compared statistically using the nonparametric Wilcoxon rank sum test.

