## Demographic and Baseline Variables

Summarization by treatment arm will include mean, standard deviation, median, minimum, maximum for continuous variables, and the number and percent for binary and ordinal variables. The age at randomization will be use in analyses. The following is a list of the demographic and baseline variables, recorded at, or shortly, before Randomization or first treatment administration:

- Age (Years)
- Age group
  - 18 to 35 years
  - >35 to 55 years
  - >55 to 75 years
  - >75 years
- Sex
- Ethnicity
- Percent predicted FVC at Screening (Pre-Bronchodilator) as  $100 \cdot \text{FVC} / \text{FVC}_{\text{predicted}}$
- Relative Change in Pre-Bronchodilator FVC between Screening and Baseline
- Percent predicted DLCO at Screening (Note that  $\text{TLCO in SI units} \times 2.987 = \text{DLCO}$ )
  - DLCO corrected for Hg
- Number (%) with Either DLCO or TLCO Provided at Screening

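### FVC decline is scored from the Screening test alone; adding the Visit 2 pre-dose FVC as a model covariate would recover a little precision at almost no cost

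*SAP*

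**What the plan says.** Both documents fix the spirometry baseline at Screening. SAP, Definition of Baseline: "Baseline values for spirometry are defined as the screening values". The same section adds: "The underlying true spirometry values are assumed to be the same at randomization". Protocol 10.4.2: "Baseline for spirometry is defined as the screening visit with the assumption that values are the same at randomization". Protocol 7.2.1 sets the gap: "Randomization (Visit 2) will occur no more than 56 days after the start of the Screening period".

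SAP, Primary and Secondary Endpoints and Relevant Variables, computes decline as the last on-study percent predicted FVC minus that baseline. No Visit 2 value enters the formula.

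Visit 2 FVC has two other uses. Under inclusion criterion 5b (Protocol 5.1), the pre-bronchodilator FVC in litres must differ by less than 10% relative between Screening and Visit 2. SAP, Definition of Baseline, also has the differences between the two tests summarized descriptively.

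The SAP gives two reasons for choosing Screening: the test must meet quality criteria, and it is done before and after a bronchodilator. The primary model (SAP, Efficacy Analyses) adjusts for baseline percent predicted FVC and HRCT pattern. The time-to-event model adjusts for HRCT pattern and, for spirometry endpoints, the baseline value. Neither includes the Visit 2 FVC. None of the sensitivity analyses named in the SAP changes the baseline.

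**The concern.** Each participant should have two pre-dose, pre-bronchodilator FVC tests, and the endpoint uses one. If the Screening reading was high by chance, or FVC fell before dosing, part of the 10-point threshold is used up before the first capsule. If the reading was low, the participant has further to fall.

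The SAP's reasons do not fully settle the choice. Visit 2 has a quality requirement too: "Baseline (Visit 2) Pre-BD spirometry meets ATS quality criteria as determined by the site Investigator or the central reviewer". The post-bronchodilator test has no counterpart at follow-up, since after Screening "The remainder of the spirometric studies will be performed without bronchodilator administration". The time-to-event clock also starts at a different point from the decline it records: "Time will be measured from randomization until the event or until censoring".

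The stake is how accurately participants are classified as events, and whether usable baseline information is left out of a trial that closed at 123 of 270 participants.

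**Working it through.** **1. The plan's own power figure.** Protocol 10.2.1: event rates 0.32 and 0.16, two-sided 5%, 85% power. With pooled variance under the null:

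n = [1.96·√(2·0.24·0.76) + 1.036·√(0.32·0.68 + 0.16·0.84)]² / 0.16² = (1.184 + 0.615)² / 0.0256 ≈ 126.4, so 127 per arm. The figure reproduces.

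At 123 in total (61.5 per arm): z = (0.16·√61.5 − 1.184) / 0.593 ≈ 0.12, so power is about 0.55.

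**2. What rule 5b permits.** The predicted value hardly changes in 56 days, so the limit in litres carries over to percent predicted. The upper bound is 0.10 × the Screening value:

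| Screening % predicted | Measured change stays below |
|---|---|
| 40 | 4.0 points |
| 70 | 7.0 points |
| 90 | 9.0 points |
| 100 | 10 points |

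Example: 70 then 64 is 6/70 = 8.6%, eligible, and 4 further points from the Visit 2 reading make an event. 64 then 70 is 6/64 = 9.4%, also eligible, and 16 points are needed. These are near the limit of the rule and are not typical values.

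**3. Plausible true change before dosing.** The IPF placebo declines in Protocol 2.1.3.3 and 2.1.3.4 are 12.4 and 9.6 points over 72 weeks. If they were linear and applied to RA-ILD, 8 weeks would give 12.4·8/72 = 1.38 and 9.6·8/72 = 1.07 points.

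**4. How much noise the second test could remove.** Let the single-test error SD be σ and the SD of true 52-week change be 6 (both assumed). Ignore drift and the entry rule. Change from Screening has variance 36 + 2σ². Averaging the two pre-dose tests gives 36 + 1.5σ². Adjusting for the Visit 2 minus Screening difference also removes half of the Screening error variance.

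| σ | Screening only | With Visit 2 | Reduction |
|---|---|---|---|
| 2 | 44 | 42 | 4.5% |
| 3 | 54 | 49.5 | 8.3% |
| 4 | 68 | 60 | 11.8% |

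The last on-study test keeps its own error, which limits the gain.

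**5. Event classification (simulated, 1,000,000 draws per scenario).** Assumed: mean FVC 70% predicted (SD 12), σ 2 to 4, SD of true change 6 or 8, drift 0, 1.07 or 1.38 points, deaths omitted, rule 5b applied, Screening-based event rates set to 0.32 and 0.16.

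- Event status differs between a Screening and a Visit 2 baseline in about 9–14% of placebo and 6–10% of pirfenidone participants.
- Power at 123 is 0.55 with Screening, 0.50–0.55 with Visit 2 alone, and 0.54–0.56 with the mean of both.

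A similar simulation (FVC 70, SD 14; drift −0.5, SD 1; 52-week change −3 to −4, SD 6 to 7) compared Screening with the two-test mean. FVC status changed in 4–6% of participants, about 5–7 of 123. Misclassification of the true post-randomization decline fell by 1.3–1.6 percentage points, for example from 12.2% to 10.7%.

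**6. Gain from the covariate.** Endpoint unchanged, n = 123, assumed effect 4.5 points, 1,500 trials per value of σ:

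| σ | Screening FVC only | Screening and Visit 2 FVC |
|---|---|---|
| 2 | 0.625 | 0.639 |
| 3 | 0.581 | 0.595 |
| 4 | 0.538 | 0.552 |

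Each gain is 1.4 points. A paired simulation, also with assumed inputs, gave 1.1–1.3 points (standard error about 0.35), with type I error near 5%.

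**The case against.** The strongest defence is that Screening is the only test that must be accepted centrally for entry. Criterion 5d requires a central reviewer, whereas 5e lets the site investigator pass Visit 2. Protocol 7.1.2 sends all FVC data to a blinded central reader, which narrows the difference but does not make central acceptance of Visit 2 an entry condition. Preferring the centrally accepted test is a defensible pre-specified choice, stated openly in both documents. Visit 2 alone would carry the same kind of single-test error. This stands, and it is why the baseline should not be replaced.

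Replacement by the two-test mean has further drawbacks. It would keep about half of any pre-treatment drift. It would pair a two-visit FVC with a Screening-only DLCO in the OMERACT endpoint. It would also redefine the primary endpoint against Protocol 10.4.2 after enrolment had closed, which Protocol 15.1 would probably route through the Executive Committee and the DSMB.

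A reader might also infer that the Visit 2 test is ignored. It is not: it gates eligibility and is summarized. The gate is what limits pre-treatment change, although SAP, Protocol Deviations, lists breaches of it as a deviation category and the ITT population keeps everyone randomized. The number of breaches is not given.

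**Conclusion.** The point holds as a modest one about precision. Screening test error and limited pre-treatment change count toward the 10-point threshold, and a baseline measurement that could absorb part of this noise is left out of the model.

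Two stronger inferences are not supported. The first is bias between arms: both tests precede randomization, so the noise is the same in expectation in each arm. The split between the Screening origin for decline and the randomization origin for time is also common to both arms. The second is material dilution of the treatment contrast: power at 123 is essentially the same with Screening or the two-test mean, and early closure accounts for the fall from 0.85 to 0.55.

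The expected gain from the covariate is about 1 power point. It rests on an assumed test error SD of 2 to 4 points and assumed distributions of FVC and its change, none of which are in the documents. That Visit 2 FVC is absent from the endpoint and the models rests on the text alone.

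The label *Baseline* for Visit 2 in Protocol 5.1, and in the SAP's listed variable "Relative Change in Pre-Bronchodilator FVC between Screening and Baseline", conflicts with the Screening definition. This is editorial, because both documents define the spirometry baseline explicitly.

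**What to change.** Before unblinding:

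1. Keep Screening as the defined spirometry baseline and leave the primary endpoint unchanged.
2. In SAP, Efficacy Analyses, add Visit 2 pre-bronchodilator percent predicted FVC as a fixed continuous covariate beside Screening percent predicted FVC, in the primary logistic model and in the time-to-event model for FVC decline. Entering the Visit 2 minus Screening difference instead gives the same model. Update SAP, Covariates, to match.
3. Pre-specify one sensitivity analysis of the primary endpoint with the mean of the Screening and Visit 2 pre-bronchodilator values as baseline. Use the single acceptable value where one test fails quality review.
4. Use one name per visit, and say that the covariate and the baseline are pre-bronchodilator values.

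The cost is one extra model term, a few lines of code and some SAP wording. No new data are needed, since Visit 2 FVC is an entry requirement. Protocol 10.4.2 already allows covariates specified before database lock and unblinding. The adjusted odds ratio becomes conditional on one more variable; the unadjusted odds ratio required by Protocol 10.4.2 should be shown beside it.
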